# 1 Protocol Overview

Study Description	The purpose of this study is to identify a tolerable dose for postpartum ketamine infusion using a maximum tolerated dose (MTD) 3+3 design. A loading dose over 1 hour will be the MTD variable to be tested, as our data suggest that ketamine side effects occur with the loading dose.
Study Population:	Patients having cesarean delivery (CD) who are either: 1) planning not to breastfeed; or 2) are receiving ketamine as part of clinical care, will be enrolled. Ketamine will be started in postpartum patients, after cord clamping.
Planned Sample Size:	The projected sample size will be a maximum of 12 patients with complete primary outcome data within the MTD 3+3 design.
Participating Institutions (if a multicenter clinical trial)	N/A

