# 3.4 Endpoints

# 3.4.1 Primary Endpoint

Maximum Tolerated Dose (MTD). The MTD will be defined as the dose at which fewer than 33% of patients experience a DLT defined by intolerability.

Tolerability (dichotomous Yes/No)

Tolerability (YES) will be defined as: lack of adverse events (adverse event defined as: severe unresolved hemodynamic effect: systolic blood pressure <80 or >160, heart rate <40 or >120).

Lack of Tolerability will be defined as presence of any adverse event (i.e., severe unresolved hemodynamic effect: systolic blood pressure <80 or >160, heart rate <40 or >120).

A **DLT** event is defined by complete infusion cessation due to intolerable side effect acceptability ratings by patient, OR the experience of an intolerable event as defined above. The escalation of dosing will be as noted in Figure 2 and is based on a modified Fibonacci sequence  $^{101,102}$  with smaller proportional increases in dose in the escalation scheme. Escalations occur until 2 in a cohort of 3 to 6 experiences DLT (i.e., until  $\geq$ 33% of patients experience DLT at that dose). The dose **below** this level estimates the MTD.

Participants will be classified as having had a DLT if any of the following conditions are met:

- Persisting (i.e., unresolved after 3 consecutive measurements within a 15-minute interval)
  hemodynamic side effects defined as below and despite treatments or minimizing
  infusion rates as specified.
  - Systolic blood pressure <80 or >160
  - Heart rate <40 or >120
- Complete infusion cessation due to intolerable side effect acceptability ratings by patient

Primary Outcomes will be measured at a minimum of every 4-hours from the start of the ketamine infusion (t = 0) for 24-hours (12-hours post infusion cessation). Additional assessments will be administered between the 4-hour measurements if any adverse event or side effect is noted by the patient.

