# 6.2 Study Drug Preparation and Dispensing

The study drug, ketamine, will be sourced by investigational (IDS) Pharmacy at UPMC Magee Women's Hospital. The infusions will be packaged and labeled for use in the clinical research study per pharmacy protocols and guidelines. Ketamine will be prepared by pharmacy with dosing instructions. There will be no blinding.

For on-site preparation and dispensing of the study drugs, the following procedures will be followed. The pharmacist of record will: maintain adequate records confirming receipt, expiration dates, or other disposition information on the investigational drug; they will record the name of the individual to whom the drug is shipped, date, quantity, and batch number. They will secure the drug in a locked storage area and monitor to ensure proper storage conditions; they will also complete regular inventory to assure accurate indication of stock on hand, as well as proper recording of stock received, dispensed, and returned. For the patients enrolled for open label pharmacokinetic studies, the pharmacist will generate a label prior to dispensing the study drug, including the date dispensed, quantity and expiration information, drug strength and dose; they will affix the label to the dispensed drug. For dispensing and drug disposition recording, they will record the date dispensed, patient initials or other identifiers, drug treatments, quantity dispensed, initials of dispenser, date and amount of patient returns documented in study records (i.e., returned drug that cannot be re-dispensed). Filing and all drug documentation will occur within study records, medical records, and logs.

Following the cesarean delivery, the initial drug administration (via IV infusion) will begin 15 minutes (± 30 minutes) after cord clamping and declaration of clinical/ hemodynamic stability by the case anesthesiologist after delivery. The maintenance dose will start 60 min (range: +15min) after the initial loading dose. The infusion will be completely stopped 12 hours after the start of infusion. The same infusion pump will follow the patient throughout the postoperative period for 12 hours until completion of the study drug. No manipulation of the infusion pump will occur by the patient. Adjustments to the rate will be at the discretion of the study team and can be physically made by study personnel qualified and trained in these procedures, or by clinical care providers under direct orders from the study team.

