# Events that Trigger Dose Adjustment Procedures:

- Persisting unresolved hemodynamic side effects defined as Systolic blood pressure <80 or >160,
   Heart rate <40 or >120^33
  - o Unresolved after 3 consecutive measurements within a 15-minute interval
- Persisting (i.e., unresolved within 1 hour of onset) side effects sedation, dizziness, lightheadedness, persistent itchiness, bad dreams, hallucinations, or other side effects that are reported as not acceptable to patients or clinicians, despite minimizing infusion rate.
- Table 1 includes procedures for dose adjustments.

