# Patient Reported Side Effects Dose Delays or Adjustments

[figure not shown]
- Side Effect Acceptability ratings are defined in section 3.4.2. Patient reported side effects (i.e., dizziness, lightheadedness, bad dreams, nausea, vomiting, itchiness, and hallucinations: all are dichotomous outcomes). These side effects will be evaluated based on patient-specific reports of how "acceptable" or "unacceptable." Patients reporting side effects and rating them as "unacceptable" will follow the dose delay or adjustment described in the Table 1. If side effects are rated "acceptable" then no dose delays or adjustments will occur.
- Figure 3 Decision Chart for Acceptability Based dose revisions.

Table 1. Loading and Maintenance Dose Adjustment Procedures:

Systolic blood pressure <80 or >160, Heart rate <40 or >120  Monitor for 5 minutes minutes for symptom resolution  Monitor for 5 minutes for symptom resolution  If event does not resolve  Hold infusion for 5 box (e.g., 0.05mg/kg/hr) and continue infusion.  If event does not resolve  Hold infusion for 5 box (e.g., 0.05mg/kg/hr) and continue infusion.  May D/C infusion and monitor subject for safety as	Event	1st Action	2 nd 1	Action	3rd /	Action	If event does not resolve
Pressure <80 or >160,   Heart rate <40 or >120   Heart rate <40 or >1							
monitor subject for safety as described in Section 7.4 and described in Section 7.4 and 7.5  Event qualifies as DLT	pressure <80 or >160,	labetalol or hydralazine per managing anesthesiologist Monitor for 5 minutes for symptom	for 5 minutes - symptom recheck at 5	(e.g., 0.05mg/kg/hr reduced to 0.025 mg/kg/hr) and continue	for 5 minutes - symptom recheck at 5 minutes:  May D/C infusion based on investigator discretion and monitor subject for safety as described in Section 7.4 and	(e.g., 0.025mg/kg/hr reduced to 0.013 mg/kg/hr) and continue	minutes of unresolved hemodynamic effect:  D/C infusion and monitor subject for safety as described in Section 7.4 and 7.5  Event qualifies

Event	1st Action	2 nd A	Action	3rd A	Action	If event does not resolve
		If event does not resolve	If the event resolves	If event does not resolve	If the event resolves	 1650.776

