If RASS -2 or below, OR Respiratory Rate is < 8	Hold infusion for 10 minutes - symptom recheck every 10 min until resolution	If no resolution within 1 hour:  D/C infusion based on investigator discretion and monitor subject for safety as described in Section 7.4 and 7.5	↓ dose by 50% (e.g., 0.05mg/kg/hr reduced to 0.025 mg/kg/hr) and continue infusion.	If no resolution within 1 hour:  D/C infusion based on investigator discretion and monitor subject for safety as described in Section 7.4 and 7.5	↓ dose by 50% (e.g., 0.025mg/kg/hr reduced to 0.013 mg/kg/hr) and continue infusion.	D/C infusion and monitor subject for safety as described in Section 7.4 and 7.5 Event qualifies as DLT
Dizziness, lightheadedness, bad dreams, persistent itchiness, hallucinations, nausea, vomiting, or other side effects rated by patient as Not Acceptable	Hold infusion for 10 minutes - symptom recheck every 10 min until resolution Supportive care medications in 9.1	If no resolution within 1 hour:  D/C infusion based on investigator discretion and monitor subject for safety as described in Section 7.4 and 7.5	↓ dose by 50% (e.g., 0.05mg/kg/hr reduced to 0.025 mg/kg/hr) and continue infusion.	If no resolution within 1 hour:  D/C infusion based on investigator discretion and monitor subject for safety as described in Section 7.4 and 7.5	↓ dose by 50%     (e.g.,     0.025mg/kg/hr     reduced to 0.013     mg/kg/hr) and     continue     infusion.	D/C infusion and monitor subject for safety as described in Section 7.4 and 7.5 Event qualifies as DLT
Nausea or Vomiting	Rescue medications as indicated in 6.6  Re-evaluate for symptom resolution 10 min after rescue medication  Hold infusion for 10 minutes - symptom recheck every 10 min until resolution	If no resolution within 1 hour:  D/C infusion based on investigator discretion and monitor subject for safety as described in Section 7.4 and 7.5	dose by 50%  (e.g., 0.05mg/kg/hr  reduced to 0.025  mg/kg/hr) and  continue  infusion.	If no resolution within 1 hour:  D/C infusion based on investigator discretion and monitor subject for safety as described in Section 7.4 and 7.5	dose by 50%  (e.g., 0.025mg/kg/hr  reduced to 0.013  mg/kg/hr) and  continue  infusion.	D/C infusion and monitor subject for safety as described in Section 7.4 and 7.5 Event qualifies as DLT

Figure 3. Dose adjustments based on patient-reported acceptability

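### The protocol defines a dose-limiting toxicity differently in 3.4.1, Table 1, 12, 12.1 and 12.3, so the section followed can decide escalation; 6.3 gives two trigger times, and the delivered load is not reported

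*Combined protocol and SAP*

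**What the plan says.** The tested quantity is the load: "A loading dose over 1 hour will be the MTD variable to be tested" (Section 1). Section 6.2 adds: "The maintenance dose will start 60 min (range: +15min) after the initial loading dose".

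Five places say what counts against a dose level:

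- **3.4.1** counts "complete infusion cessation due to intolerable side effect acceptability ratings by patient", or a hemodynamic effect that persists in spite of treatment or a lower rate. Escalation ends when 2 patients in a cohort of 3 to 6 have a DLT.
- **6.3, Table 1** puts its DLT label only in the last column, where the event has not resolved. One row carrying that label is for RASS -2 or below or respiratory rate below 8, which 3.4.1 does not list.
- **12** describes DLT as an unacceptable side effect or an adverse event, with no need for the infusion to stop.
- **12.1** bases the final dose on more than 66% of patients reporting a tolerated dose with acceptable side effects.
- **12.3** defines tolerability by unresolved hemodynamic events alone, here called serious adverse events. It reports counts and percentages.

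Section 6.3 also describes when a side effect leads to a rate reduction. Its trigger list has "Persisting (i.e., unresolved within 1 hour of onset) side effects sedation, dizziness, lightheadedness" and further effects, and for hemodynamic events "Unresolved after 3 consecutive measurements within a 15-minute interval". The text on patient reports then says that patients who rate an effect unacceptable "will follow the dose delay or adjustment described in the Table 1". That table is headed "Table 1. Loading and Maintenance Dose Adjustment Procedures". For unacceptable effects its first action is "Hold infusion for 10 minutes - symptom recheck every 10 min until resolution", followed by a 50% cut if the event resolves.

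**The concern.** In a 3+3 design with cohorts of 3 to 6, one or two patients decide whether the next cohort gets a higher dose. The definition of a countable event therefore carries the whole primary endpoint. Here the same patient can be a DLT in one section and not in another, so escalation at the bedside and the analysis in Section 12 could rest on different counts.

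Under 12.3 there is a further effect: patients who stop the infusion completely because they find the effects unacceptable are DLTs in 3.4.1 but would drop out of the primary analysis.

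The two trigger times in 6.3 raise a smaller, related issue. They determine whether a side effect during the loading hour changes how much of the tested dose is given, and no planned output shows how much was given.

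**Working it through.** **Step 1. One cohort, five rules.** Inputs are the definitions above and the stated thresholds (33% and 66%); no event rates are assumed. In each scenario the third patient has no event and nobody has a hemodynamic event.

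- A: two of three rate an effect unacceptable, are cut 50%, and recover.
- B: two of three rate effects unacceptable and end in complete cessation through the last column of Table 1.
- C: two of three reach final discontinuation for respiratory rate below 8 without an unacceptable rating.

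| Rule | A | B | C |
|---|---|---|---|
| 3.4.1 list | 0/3 | 2/3 | 0/3 |
| Table 1 label | 0/3 | 2/3 | 2/3 |
| Section 12 | 2/3 | 2/3 | 2/3, as adverse events |
| 12.1 (share acceptable) | 1/3 | 1/3 | unclear |
| 12.3 | 0/3 | 0/3 | 0/3 |

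2/3 = 66.7%, at or above 33%, so escalation stops. 0/3 means escalate. For 12.1, 1/3 = 33.3%, which is not above 66%, so the dose is not tolerated. No scenario gets the same answer from all the rules.

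**Step 2. Trigger time and delivered load.** Assume the effect appears at 15 or 30 minutes, which are scheduled diary times in Section 7, and is rated unacceptable then. Take the shortest hold in Table 1 (10 minutes), one halving, and a 60-minute load.

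If Table 1 acts on the rating, the delivered share is [t + 0.5 × (60 − t − 10)] / 60:

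- t = 15: (15 + 0.5 × 35) / 60 = 32.5 / 60 = 54%
- t = 30: (30 + 0.5 × 20) / 60 = 40 / 60 = 67%

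At the 0.2 mg/kg/hr ceiling these are 0.2 × 0.542 = 0.108 mg/kg and 0.2 × 0.667 = 0.133 mg/kg, against 0.2 mg/kg assigned. A longer hold gives less.

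If the 1-hour persistence trigger applies, the reduction falls at 15 + 60 = 75 or 30 + 60 = 90 minutes. The 60-minute load is complete by then, so 100% is delivered.

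**Step 3. How such a patient is counted.** The infusion was not stopped, so 3.4.1 is not met; the event resolved, so Table 1's last column is not reached. On the visible text the patient is a non-DLT at the assigned level.

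**Step 4. Frequency.** No rate of reductions in the loading hour is given. The nearest figure, 1/8 = 12.5% of earlier patients with a rate below 0.05 mg/kg/hr, is called unrepresentative in 6.3 itself. No escalation probability is therefore calculated.

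**The case against.** The best defense is that 3.4.1 plainly governs. Section 4 points to it for the DLT definition, Section 12 reads as shorthand for it, and 12.3 repeats its hemodynamic half. Table 1 says outright that the sedation and respiratory discontinuations qualify, and nothing in 3.4.1 denies it. The version history fits an editing lapse: version 7.0 lists 3.4.1, 6.3 and Table 1 for the cessation criterion, but 12.3 only for the blood pressure cutoff. This is a good reason to adopt 3.4.1 as the single source. It does not repair 12.3, the section that governs analysis of the primary endpoint, or the mismatch between Table 1 and 3.4.1.

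On delivered load, the plan already collects relevant data. Any reported side effect or adverse event prompts a blood draw (Sections 4 and 7, Appendix 2), and Cmax, AUC and Css are to be correlated with DLTs. That is useful exposure information, but it is not the dose delivered.

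A reader might infer that the plan credits patients with tolerating a full load they never received, and so overstates the MTD. The documents do not support that. No sentence says so, and Figures 2 and 3, where a rule on reduced loads could sit, are not shown in the copy reviewed. For effects starting at 15 or 30 minutes the shortfall vanishes under the 1-hour trigger. For hemodynamic events the trigger and the DLT share the same persistence wording, so a patient who reaches the trigger may already be a DLT.

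A reader might also infer that reductions should count against a level, or that the MTD should be relabelled. Allowing titration before declaring a DLT is a legitimate choice, and a threshold on reductions would be a new decision rule.

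**Conclusion.** The conflict in the primary-endpoint rules is established from the text, without assumed rates. In scenario A the answer is escalate (3.4.1, 12.3), stop (Section 12) or not tolerated (12.1); in scenario B, 12.3 loses two DLTs that 3.4.1 counts. It should be corrected, because it can change both escalation and the reported MTD. The two trigger times for side effects in 6.3 are likewise a conflict in current text.

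The delivered-load point is a cheap improvement, not a demonstrated flaw in the MTD. It holds for patient-rated effects that resolve. Its size, about 54% to 67% of the load after one halving, rests on a 15- or 30-minute event, a 10-minute hold and action on the rating. The alternative trigger gives 100%. How often this would happen is unknown.

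**What to change.** 1. Make 3.4.1 the only DLT definition, add Table 1's final discontinuations for RASS -2 or below or respiratory rate below 8, and have 12, 12.1 and 12.3 refer to it in place of their own wording.
2. State one trigger time for side-effect reductions in 6.3. Table 1 already uses 1 hour as the limit for non-resolution before discontinuation, so the 1-hour wording could be confined to that step if action on the rating is what is intended.
3. From the pump record, report mg/kg delivered in the loading hour by patient and dose level, with each hold or reduction and its reason, as a descriptive table beside the MTD. Add no flag threshold and leave the escalation rule as it is.

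The cost is wording edits in one amendment, which needs IRB approval under 14.1, plus pump-record capture for about 12 patients and one table. Unless the sponsor chooses a trigger time that differs from current practice, bedside care is unchanged.

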# 3.4.2 Secondary Endpoints

Patient-reported *side effect* acceptability ratings, defined below Peripartum pain scores, defined in Appendix 1

Peripartum depression scores, defined by Edinburgh Postnatal Depression Score (EPDS)

# Side Effect Acceptability Ratings

Any reported side effects are rated by patients. Patient reported side effects (i.e., dizziness, lightheadedness, bad dreams, nausea, vomiting, itchiness, and hallucinations: all dichotomous outcomes) will be evaluated based on patient-specific reports of how "acceptable" or "unacceptable" the side effects are for continued or future use of the study medication. Patient-reported acceptability is defined based on theoretical framework of acceptability and focused on constructs of Burden ("Would experiencing side effects keep you from participating in this intervention (ketamine) again?" yes/no) and Affective Attitude ("Based on your experience with this medication, would you be willing to participate in this intervention (ketamine) again?" yes/no).

- 1. Acceptability is the absence of patient-centered unacceptable side effects. Patients with side effects who report that the side effects were "acceptable" on digital diary will be counted as having confirmed **side effect** acceptability ratings, regardless of the presence of any side effects to the ketamine dose. Patient-reported acceptability is defined as a "yes" to Affective Attitude with a "no" to Burden.
- 2. Unacceptability is any patient report of unacceptable side effects, defined as any positive response on the digital side effect diary rated unacceptable by the patient. Either a negative response to Attitude, or a positive response to Burden, will define patient unacceptability.

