In addition to its analgesic effects, ketamine use for depression treatment promotes fast, effective depression symptom reductions, a robust effect occurs from 4-72 hours post-infusion (0.5 mg/kg over 40 min) in patients with MDD; this dose is commonly used for depression. The antidepressant effect lasts beyond psychotomimetic symptoms, which peak during the infusion and return to baseline within 1-2 hours. These findings contrast traditional antidepressants whereby only 1/3 of patients become symptom-free after 7 weeks of treatment with SSRI. A widely cited trial of 205 ketamine doses (0.5mg/kg, 40 min) for depression concluded ketamine was, "safe and well- tolerated" but did not probe patient acceptability of side effects. Dose-dependent side effects are common, with a high incidence of vertigo, nausea, sedation, and dissociation in intranasal dosing to plasma levels similar to an IV dose of 0.5 mg/kg over 40min. These dose-dependent side effects preclude widespread use in the peripartum population. Identifying ketamine dose tolerability in a post-CD population has the potential to improve treatment of postoperative pain as well as mood-related outcomes of chronic pain such as comorbid onset of PPD. This work will

Defining postpartum ketamine PK is critical to understanding the potential role of ketamine for PPD prevention, and to understanding the plasma ketamine concentration time profile with its maximum tolerated dose. There are no PK/PD models for ketamine-induced side effects or analgesia, although there are isolated reports of ketamine side effects with plasma concentrations. Available trials that conclude ketamine is "well tolerated" did not query patient perspectives in acceptability. The duration of ketamine exposure may be important as well, given that subcutaneous administration may have greater antidepressant duration than intravenous administration of the same dose, despite lower

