#### Side Effect Acceptability Ratings.

Our existing and previously tested **digital diary** will automate alerts for questions about side effects after infusion start at 15-, 30-, 60- minutes, and every 4 hours in the first 24 hours after infusion start (Figure 1, section 1.1). The diary has been tested and used by our group in previous work; alerts coincide with RASS assessments and similar timing of clinical assessments for routine CD nursing care and monitoring (i.e., is not more burdensome or intrusive to patients than routine clinical post-CD care). The digital diary will assess side effects

(i.e., dizziness, lightheadedness, bad dreams, nausea, vomiting, itchiness, and hallucinations: all dichotomous outcomes). Any positive response to any item will trigger the subject to rate their acceptability of side effects in the following way. Patient-reported acceptability is defined based on theoretical framework of acceptability and focused on constructs of *Burden* ("Would experiencing side effects keep you from participating in this intervention (ketamine) again?" yes/no) and *Affective Attitude* ("Based on your experience with this medication, would you be willing to participate in this intervention (ketamine) again?" yes/no). Either a negative response to Attitude, or a positive response to Burden, will define patient unacceptability.

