#### 8 Potential Risks and Benefits

# 8.1 Reasonably Foreseeable Risks Related to Study Drug

Common side effects of ketamine are sedation, dizziness, lightheadedness, bad dreams, hallucinations, euphoria, dysphoria, nausea, vomiting. These risks are minimized by using doses below the doses that we typically see these side effects. Seriousness: mild to moderate.

Uncommon effects of ketamine include hypertension or hypotension, tachycardia, or bradycardia. These risks are minimized as much as possible by using doses below the doses that we typically see these effects. If these effects are noted, the drug will be stopped until the effects dissipate. Should the effects not dissipate, the PI will evaluate and determine whether the patient requires additional care. If these uncommon effects are experienced, an SAE log will be completed and the IDSMB and IRB notified. Seriousness: mild to moderate

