Appendix 2 – Schedule of Perinatal, Surgical, and Infusion-Specific Research Activities

			Study Visit# 1; Day 0—Delivery/Cesarean Surgery -24 hours post-surgery												
Screening & Baseline Measures	screening seline ures	Presurgical Intake T-1 hour If not completed at baseline	Cesarean Surgery	Ketamine Infusion 15-45 minutes Post	12-hour Ketamine Infusion 12-hour post-infusion								fusion		
			Cesarear		15 Minutes	30 Minutes	Hour 1	Hour 4	Hour 6	Hour 8	10Hour	Hour 12	Hour 16	Hour 20	Hour 24
Informed consent	Х														
Demographics and Medical History (inc. Opioid use in hospital)	Х	Х													
Concomitant medication review	Х	X													
Administer study intervention				X											
Maternal Plasma Samples a							Χ		Χ		Χ	X			
Adverse event review b				X											X
Surgical operative survey				Х											
Pain Intensity	Х	X													
Pain Unpleasantness	X	X													
PROMIS-PI	X	X													
EPDS	Х	X													
PSS	X	X													
SF-MPQ	Х	X													
RASS b					Х	Χ	Χ	Х		X	X	Х	Х	Χ	X
Patient Vitals b		X		Х	X	Х	Χ	Х	Х	Χ	Χ	Х	Χ	Χ	X
LSD Short b					Х	Х	Х	Х		Х	Х	Х	Х	Х	Х
Side Effect Diary and Patient Acceptability b					Х	Х	Х	Х		Х	Х	Х	Х	Х	Х

<sup>a Maternal Plasma Sampling includes analysis of Ketamine, ketamine metabolites (Nor-Ketamine & DKNK), Ketamine R- & S-isomers, cortisol, prolactin, and CYP3A and CYP2B6 enzymes

b Adverse Events will result in collection of RASS, LSD short form, Patient vitals, Patient Acceptability ratings, and Maternal plasma sampling at any point between infusion start (t = 0) to 24-hours post-infusion start. LSD score of >8 will trigger a notification to staff and investigator to prompt bedside evaluation.

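### The diary list that opens the acceptability questions omits sedation and dysphoria, and the plan does not say whether RASS or LSD findings open them or how an unrated patient is counted

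*Combined protocol and SAP*

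**What the plan says.** Section 3.4.2 (Side Effect Acceptability Ratings) defines the rated effects: "Any reported side effects are rated by patients. Patient reported side effects (i.e., dizziness, lightheadedness, bad dreams, nausea, vomiting, itchiness, and hallucinations: all dichotomous outcomes". The patient-reported part of Section 6.3 and the acceptability part of Section 7 give the same seven items, each time introduced by i.e. and so written as a closed list. Section 7 then states: "Any positive response to any item will trigger the subject to rate their acceptability of side effects in the following way". What opens is a pair of yes/no questions, Burden and Affective Attitude.

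Section 8.1 gives the protocol's own risk list: "Common side effects of ketamine are sedation, dizziness, lightheadedness, bad dreams, hallucinations, euphoria, dysphoria, nausea, vomiting".

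Sedation and dysphoria are measured in other ways. Section 7 (Side Effects) puts RASS and the LSD short form among the diary questions, and Appendix 2 schedules both at the same times as the side effect diary. The only stated consequence of a high dysphoria score is in footnote b of Appendix 2: "LSD score of >8 will trigger a notification to staff and investigator to prompt bedside evaluation". The same footnote says that adverse events lead to collection of acceptability ratings.

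Section 3.4.2 gives two descriptions of acceptability. One treats the lack of any unacceptable effect as acceptable. The other requires a yes to Attitude together with a no to Burden.

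**The concern.** The rationale in Section 2.2 is that earlier studies judged ketamine well tolerated without asking patients whether its side effects were acceptable. Acceptability is therefore the secondary objective (Section 3.3.2). It is also one of the two routes to a DLT, through complete cessation of the infusion for unacceptable ratings (Section 3.4.1), and Section 12.1 brings it into the primary outcome.

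As Sections 3.4.2 and 7 are written, the diary asks about itch, which Section 8.1 does not list, and then asks whether it is acceptable. It does not do the same for sedation or dysphoria, which Section 8.1 does list. If a patient finds one of these unacceptable and has no listed effect, the plan has no sure way to record it. An omission of this kind can only lose unacceptable reports. The error would run towards higher acceptability, fewer patient-rated DLTs and possibly a higher MTD.

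**Working it through.** The plan states no figure that depends on this point, so there is none to reproduce. The check sets the lists side by side.

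| Effect | On the list that opens the questions (3.4.2, 6.3, 7) | Common in 8.1 | In the diary per 5.5, 11.1, 11.2 | Other scheduled measure |
|---|---|---|---|---|
| Sedation | no | yes | yes | RASS |
| Dysphoria | no | yes | through the LSD short form | LSD short form |
| Euphoria | no | yes | no | none stated |
| Itch | yes | no | yes (as pruritus) | none stated |
| Dizziness, lightheadedness, nausea, vomiting, bad dreams, hallucinations | yes | yes | yes | none stated |

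**Counts.** Section 8.1 names 9 effects, of which 6 are on the seven-item list, so 9 − 6 = 3 have no prompt (sedation, euphoria, dysphoria). The withdrawal sections (5.5, 11.1, 11.2) give 9 diary components, so 9 − 7 = 2 are additional to the seven (sedation and the LSD short form). The protocol thus describes the contents of one diary in two ways.

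**Following one patient.** Suppose she has only dysphoria, or only sedation milder than RASS −2, and finds it unacceptable.

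1. Seven-item list: she answers no to every item, so the questions do not open.
2. RASS or LSD: she is assessed at every diary time, but no text says the result opens the questions. An LSD score above 8 is stated to bring staff to the bedside and nothing further.
3. Appendix 2, footnote b: a rating follows if her symptom is an adverse event. Under the broad definition in Section 10 it is, and Section 10.1 gives both effects as Grade 1 examples. Under Section 3.4.1, adverse event means a severe unresolved hemodynamic effect, and then it is not. The footnote does not say which meaning applies.
4. Section 6.3 and Table 1: Section 6.3 names sedation among effects reported as not acceptable, and both places have an open category for other effects. Both presuppose that the patient or clinician has already judged the effect not acceptable, and no diary item elicits that judgement from her.
5. Scoring: under the first description in Section 3.4.2 she is acceptable, because there is no unacceptable report. Under the second she has no rating, because neither question was answered. No rule says which is used.

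**Illustration on assumed rates, not an estimate.** If a proportion q of patients had an unacceptable effect of only these kinds and were not asked, the chance of missing at least one among 12 is 1 − (1 − q)^12. That gives 46% for q = 5%, 72% for q = 10% and 93% for q = 20%.

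For DLTs, the usual 3+3 probability of escalating past a level with DLT rate p is (1 − p)³ + 3p(1 − p)²(1 − p)³. At an assumed true rate of 33%:

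| DLTs not captured | Rate seen by the rule | Probability of escalating |
|---|---|---|
| none | 0.330 | 0.301 + 0.134 = 0.43 |
| 10% | 0.33 × 0.90 = 0.297 | 0.50 |
| 25% | 0.33 × 0.75 = 0.2475 | 0.61 |
| 50% | 0.33 × 0.50 = 0.165 | 0.78 |

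This shows how sensitive the 3+3 rule is to missed events. The documents give no basis for choosing a row.

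**The case against.** A reader might infer that a patient with only sedation, dysphoria or dissociation is never asked and is scored as acceptable. The documents do not support that, for these reasons.

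- **Never asked.** Sections 5.5, 11.1 and 11.2 place sedation and the LSD short form inside the diary. If they are diary items, the Section 7 trigger may already reach them. Footnote b of Appendix 2 offers a second route. RASS and LSD are actively solicited, and Section 7 sends automated alerts for abnormal responses. What is missing is an explicit link to the rating.
- **Scored as acceptable.** This follows from only one of the two descriptions in Section 3.4.2.
- **Size of the group.** Burden and Attitude ask about side effects and the medication in general. One yes to dizziness, nausea or any other listed item lets the patient's answer reflect sedation or dysphoria as well. Only a patient with unlisted effects alone can be missed.
- **Effect on the MTD.** RASS −2 or below has its own row in Table 1, leading to a DLT without any acceptability rating. A patient-rated DLT also requires that the infusion be stopped completely, so a missed rating is not automatically a missed DLT.
- **Dissociation.** It appears only in the background, "with a high incidence of vertigo, nausea, sedation, and dissociation in intranasal dosing to plasma levels similar to an IV dose", and is absent from the Section 8.1 list. Hallucinations are prompted.

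All of this stands and limits the point. It does not close the gap for milder sedation and for dysphoria. The lists disagree, the adverse-event route depends on which definition staff apply, and Section 3.4.2 ties unacceptability to a positive diary response, so an effect mentioned outside the diary may not count.

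**Conclusion.** The point holds as a gap in measurement and an inconsistency between sections. Sedation and dysphoria are absent from the closed list that opens the acceptability questions, no text connects RASS or LSD results to those questions, and no rule says how a patient without a rating is counted. A patient whose only effects are milder sedation or dysphoria is not systematically asked.

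Any resulting undercount would favour acceptability and reduce patient-rated DLTs. Its size cannot be estimated from the documents, and the probabilities above rest entirely on assumed rates. A reader might infer a demonstrated upward bias in the MTD. The text does not support that, because the exposed group is narrow and deeper sedation has its own DLT path.

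The conclusion rests on the protocol text. Figures 1 and 3 and the diary instrument could not be seen, and the instrument may already contain the missing items or link. Since the measure is the secondary objective and the correction is small, the change should be made.

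**What to change.** 1. Use one diary item list in Sections 3.4.2, 5.5, 6.3, 7, 11.1 and 11.2. Include yes/no items for sedation and dysphoria, and optionally one for feeling detached or unreal.
2. State in Sections 3.4.2 and 7 and in footnote b of Appendix 2 that a positive answer to any of these items, or an LSD score above 8, opens the Burden and Attitude questions. State which meaning of adverse event the footnote uses.
3. State one scoring rule for patients with no rating, and report their number beside the acceptability percentages in Section 12.4.
4. Reconcile the adjustment triggers in Section 6.3 and Table 1 with the single list. An unacceptable rating leads into those procedures, so how they apply to added items is for the trial's clinical team to settle. No clinical rule is proposed here.

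The cost is a wording amendment, two or three yes/no items in an existing digital diary and a few seconds more per entry. Measured acceptability may come out slightly less favourable.
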